4.9. Randomization and blinding of patients

- Patients that fulfill the inclusion criteria and do not fulfill any of the exclusion criteria will be randomly allocated to either rESWT plus C-E drugs (n=50), rESWT alone (n=50) or C-E drugs alone (n=50), respectively (sample size is addressed in Section 5.1. *Power analysis* below).
- Randomization will be performed as described by Rompe et al. (2008) in a randomized, controlled study on rESWT for Achilles tendinopathy. Specifically, a computerized random-number generator will be used to formulate an allocation schedule. Subjects will be randomized to either treatment (rESWT plus C-E drugs, rESWT alone or C-E drugs alone), with use of the method of randomly permuted blocks. The randomization scheme will be generated with the use of the website www.randomization.com. One hundred and fifty patients will be randomized into five blocks. A medical assistant at the Department of Pain Medicine at the First Affiliated Hospital of Zhejiang University will allocate interventions by means of opaque sealed envelopes that will be marked according to the allocation schedule. The medical assistant will be unaware of the size of the blocks.
- The randomized intervention assignment as outlined above will be concealed from both patients and health care staff until recruitment will be complete and irrevocable.

- Neither patients nor therapists will be blinded in the proposed study. The therapist will be the person who will administer rEWST to the patient.
- The assessor will be blinded in the proposed study. The assessor is the person who will assess treatment success during follow up.

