4.11. Outcome of Interest

4.11.1. Primary clinical outcome and definition of treatment success

- Primary clinical outcome will be the Pain Self-Efficacy Questionnaire (PSEQ) score (Nicholas, 1989).
 - Patients will be asked to rate how confident they are at the time of examination despite the presence of their pain in performing the following activities, listed by selecting a number on a 7 point scale where 0 equals “not at all confident” and 6 equals “completely confident”:
 - I can enjoy things, despite the pain.

- I can do most of the household chores (e.g. tidying-up, washing dishes, etc.), despite the pain.
- I can socialize with my friends or family members as often as I used to do, despite the pain.
- I can cope with my pain in most situations.
- I can do some form of work, despite the pain (“work” includes housework, paid and unpaid work).
- I can still do many of the things I enjoy doing, such as hobbies or leisure activity, despite the pain.
- I can cope with my pain without additional medication (next to rESWT plus C-E drugs, rESWT alone or C-E drugs alone, respectively).
- I can still accomplish most of my goals in life, despite the pain.
- I can live a normal lifestyle, despite the pain.
- I can gradually become more active, despite the pain.
- Scores on the PSEQ may range from 0 to 60, with higher scores indicating stronger self-efficacy beliefs.
- A point score change of 11 points for the PSEQ score corresponds to the minimal clinically important difference (MCID), defined as the smallest difference that patients and clinicians perceive to be worthwhile when treating chronic non-specific low back pain (Maughan and Lewis, 2010).
- According to Maughan and Lewis (2010) the PSEQ score is responsive to clinically important change over time.
- The PSEQ score will be collected at baseline and at all follow-up examinations, i.e., two weeks, four weeks, 12 weeks and 24 weeks after baseline.
- In the present study treatment success is defined as individual improvement of the PSEQ score by more than 20 points at 12 weeks after baseline.

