4.12. Blinding of therapists and assessors

- Therapists applying the treatments will not be blinded. This will be done because even when using coded “active” and “placebo” handpieces in a study on ESWT, blinding of ESWT therapists can only be achieved when another person prepares the device before rESWT or sham treatment. This, however, is almost impracticable and has not been done in any of the more than 100 studies on rESWT and fESWT listed in the PEDro database (Schmitz et al., 2015). The solution to this issue is a strict, standardized way of interaction between the ESWT therapist and the patients, irrespective of treatment allocation (as mentioned in a study by Buchbinder et al., 2002). This approach will also be applied in the proposed study.
- All assessments before the first treatment (baseline) and during the follow-up period will be performed by assessors blind to the intervention.

5. Follow-up and statistical analysis

- Follow-up will be the same for all study patients.
- The design of the proposed study guarantees that there will be full compliance with the allocated treatment and, thus, no contamination of one group.
- The patient's age, gender, body mass index, job occupation and duration of non-specific low back pain are potential confounding factors when treating chronic non-specific low back pain with rESWT. Normal distribution of these data will be tested using the D'Agostino-Pearson omnibus test. In case of passing the normality test we will report mean and standard error of the mean of these variables; otherwise we will report inter-quartile ranges of these variables. Comparison between groups will be performed with ANOVA followed by Bonferroni post tests for pairwise comparisons in case of passing the normality test, or the nonparametric Kruskal-Wallis test followed by Dunns tests for pairwise comparisons in case of not passing the initial normality test.
- As outlined in Section "Primary clinical outcome and definition of treatment success" above, the primary clinical outcome will be the PSEQ score at 12 weeks after baseline. Treatment success (i.e., number of patients with individual improvement of PSEQ score by more than 20% at 12 weeks after baseline) will be tested with Fisher's exact test.

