- As outlined in Section "Secondary clinical outcomes" above, the secondary clinical outcomes will be the NRS score, OLDPDQ score, PHQ-9 score, Cobb's angle, vertebral body and intervertebral disc wedging and facet joint angles. Each secondary clinical outcome will return a single data point at each time of follow-up examination. The NRS score, OLDPDQ score and PHQ-9 score are not normally distributed data. Accordingly, we will report inter-quartile ranges of these variables. Comparison between groups will be performed using the nonparametric Kruskal-Wallis test followed by Dunns tests for pairwise comparisons. Normal distribution of the Cobb's angle, vertebral body and intervertebral disc wedging and facet joint angles will be tested using the D'Agostino-Pearson omnibus test. Comparison between groups will be performed with ANOVA followed by Bonferroni post tests for pairwise comparisons in case of passing the normality test, or the nonparametric Kruskal-Wallis test followed by Dunns tests for pairwise comparisons in case of not passing the initial normality test.
- The probability value of less than 0.05 ($p\text{-value} < 0.05$) will be considered as statistically significant (Lang & Secic, 2006).

- All calculations will be performed using GraphPad Prism (version 5.00 for Windows, GraphPad Software, San Diego, CA, USA).
- All main conclusions of the study will be based on analyses of intention to treat rather than analyses of treatment. Note that there are various available methods for handling missing data in clinical trials (European Medicines Agency, 2010). In case of missing data (i.e., in case a patient will withdraw or will be lost during the treatment or the follow-up periods) we will determine together with the statistics experts at the Institute for Medical Informatics, Biometry and Epidemiology (IBE) at the Ludwig-Maximilians-University of Munich (Munich, Germany) the most appropriate method for performing analyses of intention to treat. After randomization and the first treatment with respectively rESWT plus C-E drugs, rESWT alone or C-E drugs alone, no patient will be replaced.
- All efforts will be made to keep the proportion of patients lost to follow-up too small to affect the main findings of the proposed study.
- Patient-centered care throughout the proposed study will ensure that no patients will be lost to follow-up, or the number of patients lost to follow-up will be so small that findings would be unaffected by their inclusion.

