5.1. Power analysis

In none of the studies on ESWT for non-specific low back pain performed so far (Nedelka et al., 2014; Lee et al., 2014; Han et al., 2014; Moon et al., 2016) a definition of treatment success was defined, a Power analysis was reported and the PSEQ score was used to assess clinical outcome. Accordingly, these studies are only of very limited use for the purpose of performing a Power analysis of the proposed study.

Based on anecdotal evidence from several therapists in Europe and Latin America who have been using rESWT for non-specific low back pain for more than a decade we hypothesize that treatment of chronic non-specific low back pain with rESWT alone as described above will result in a success rate of approximately 70%, and the combination of rESWT and C-E drugs in a success rate of approximately 85%. Furthermore, based on our own experience we hypothesize that treatment of chronic non-specific low back pain with C-E drugs alone as described above will result in a success rate of only approximately 35%

On this basis we performed a Power analysis, both for a percentage of 35% as well as for various other percentages (ranging between 10% and 99.9%) of patients with treatment success when treated with C-E drugs alone, accounting for a two sided-confidence interval of 95% (and, thus, a type-1 error rate of 5%). Calculations were performed using the software Open Source Epidemiologic Statistics for Public Health (www.openepi.com). The results are summarized in Tables 7 and 8.

Table 7. Power for the proposed RCT on rESWT plus C-E drugs or rESWT alone for chronic non-specific low back pain, accounting for a two sided-confidence interval of 95% and a percentage of patients with treatment success of 40% when treated with C-E drugs alone (assuming n=50 patients per group).

Percent of patients treated with rESWT plus C-E drugs or C-E drugs alone with treatment success [%]	Power based on Normal approximation [%]	Power based on Normal approximation with continuity correction [%]
99.9	100	100
90	100	100
85	100	100
80	99.8	99.6
70	95.0	92.4
60	71.3	63.5
50	32.7	25.2
40	7.2	3.5
35	1.1	0

Table 8. Power for the proposed RCT on rESWT plus C-E drugs for chronic non-specific low back pain, accounting for a two sided-confidence interval of 95% and a percentage of patients with treatment success of 70% when treated with rESWT alone (assuming n=50 patients per group).

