Percent of patients treated with rESWT plus C-E drugs or C-E drugs alone with treatment success [%]	Power based on Normal approximation [%]	Power based on Normal approximation with continuity correction [%]
99.9	99.3	98.3
90	71.2	61.2
85	43.4	33.4
80	20.9	14.2
70	1.1	0

Furthermore, we calculated the minimum sample size in both groups (rESWT, control) that would be necessary for detecting a difference in treatment success between

- the patients treated with rESWT plus C-E drugs and the patients treated with C-E drugs alone,
- the patients treated with rESWT alone and the patients treated with C-E drugs alone, and

- the patients treated with rESWT plus C-E drugs and the patients treated with C-E drugs alone,

accounting for a two sided-confidence interval of 95% and a power of 0.8. Calculations were also performed using the software Open Source Epidemiologic Statistics for Public Health (www.openepi.com). The results are summarized in Tables 9 and 10.

Table 9. Sample size in the proposed RCT on rESWT plus C-E drugs or rESWT alone for chronic non-specific low back pain, accounting for a two sided-confidence interval of 95% and a power of 0.8. The percentage of patients with treatment success when treated with C-E drugs alone was set at 40%.

Sample size of both groups (rESWT, placebo) according to...				
Percent of patients with treatment success when treated with rESWT plus C-E drugs or rESWT alone [%]	Kelsey et al. (1996)	Fleiss et al. (2003)	Fleiss et al. (2003) with continuity correction	
99.9	10	8	11	
90	15	14	17	
85	19	17	22	
80	24	23	28	
70	44	42	49	
60	99	97	107	
50	389	388	408	
45	1502	1501	1540	

Table 10. Sample size in the proposed RCT on rESWT plus C-E drugs for chronic non-specific low back pain, accounting for a two sided-confidence interval of 95% and a power of 0.8. The percentage of patients with treatment success when treated with rESWT alone was set at 70%.

Sample size of both groups (rESWT, placebo) according to...				
Percent of patients with treatment success when treated with rESWT plus C-E drugs or rESWT alone [%]	Kelsey et al. (1996)	Fleiss et al. (2003)	Fleiss et al. (2003) with continuity correction	
99.9	23	22	28	
90	63	62	72	
85	122	121	134	
80	297	296	316	
75	1221	1220	1259	

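### The unadjusted Fisher's exact test on treatment success is valid but gives up some power: pairwise it runs at about 2.4–3.5%, and baseline PSEQ, already collected, is never a covariate

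*Combined protocol and SAP*

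**What the plan says.** Section 5 (Follow-up and statistical analysis) names PSEQ at 12 weeks as the primary outcome and says that the number of treatment successes "will be tested with Fisher's exact test". It mentions no covariate, stratification or model, and does not say whether the test is pairwise or a single 3×2 test. "The probability value of less than 0.05" is the significance threshold, and no multiplicity rule is attached to the success comparisons.

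The same section says that age, gender, body mass index, occupation and pain duration "are potential confounding factors when treating chronic non-specific low back pain with rESWT". Their only planned use is a between-group comparison (ANOVA or Kruskal-Wallis with post tests).

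Section 4.11.1 says: "The PSEQ score will be collected at baseline and at all follow-up examinations". It defines success as a gain of more than 20 points, on a scale from 0 to 60. Section 5 writes the threshold as more than 20 percent instead.

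Section 5.1 works only with pairs of arms. It assumes success rates of 70% (rESWT), 85% (combination) and 35% (C-E drugs), with 40% for C-E drugs in Table 9. It concludes that 49 per group suffices for the two comparisons against C-E drugs and that combination versus rESWT would need 134.

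**The concern.** Two features of the planned test cost power. First, Fisher's test conditions on both margins, so at 50 per arm it rejects less often than 5% under the null. Second, success is a gain from baseline on a bounded scale, so a patient's starting score partly decides whether success is possible, and the planned test cannot use that information.

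Testing the five named factors for baseline differences does not fill the gap. In a randomised trial such a test does not remove the effect of a chance imbalance, and the plan attaches no action to its result. At stake are the precision of the success comparison and its robustness to imbalance, mainly for combination versus rESWT, which is part of the hypothesis in Section 2 and is the pair with least power.

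**Working it through.** **Inputs from the documents.** 50 per arm (Section 4.9); two-sided 5% and power 0.8 (Section 5.1); success rates as above.

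**1. The plan's sample sizes.** n = [1.960·√(2p̄q̄) + 0.842·√(p₁q₁ + p₂q₂)]² / (p₁ − p₂)², where p̄ is the mean of the two rates. The continuity-corrected size is (n/4)·[1 + √(1 + 4/(n·|p₁ − p₂|))]².
- 40% vs 70%: (1.960 × 0.7036 + 0.842 × 0.6708)² / 0.09 = 41.97, so 42; corrected 48.4, so 49.
- 70% vs 85%: (1.960 × 0.5906 + 0.842 × 0.5810)² / 0.0225 = 120.5, so 121; corrected 133.5, so 134.

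Both agree with Tables 9 and 10. The plan's 49 and 134 are the continuity-corrected values. Exact Fisher power at these sizes is 81.5% (n = 49) and 80.6% (n = 134).

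**2. Exact size of pairwise Fisher at n = 50** (all 51 × 51 outcomes, common success rate p):

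| p | 35% | 40% | 50% | 70% | 85% |
|---|---|---|---|---|---|
| size | 3.04% | 3.21% | 3.52% | 3.07% | 2.39% |

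**3. Exact power at n = 50.** Boschloo's test uses the Fisher p-value as its statistic. Its critical value here is 0.0693, with maximum size 4.87%, so it rejects whenever Fisher's test does.

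| Pair | Fisher | Boschloo |
|---|---|---|
| C-E 35% vs combination 85% | 99.95% | 99.98% |
| C-E 35% vs rESWT 70% | 93.1% | 94.0% |
| C-E 40% vs rESWT 70% | 82.9% | 85.5% |
| rESWT 70% vs combination 85% | 35.4% | 40.6% |

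**4. Why baseline PSEQ matters.** A gain above 20 points with a ceiling of 60 needs a baseline below 40. Under the percentage wording, 1.2 × baseline must stay below 60, so baseline must be below 50.

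For imbalance, assume a baseline SD of 10, a slope of follow-up on baseline of 0.5 and a residual SD of 10.5. One standard error of the between-arm baseline difference is 10 × √(2/50) = 2 points. It shifts the mean gain by (1 − 0.5) × 2 = 1 point. The SD of the gain is √(0.5² × 10² + 10.5²) = 11.6, so near a 50% success rate the shift is about 0.399 × 1/11.6 = 3.4 percentage points, before any ceiling effect.

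**5. Baseline adjustment (simulation).** The documents give no PSEQ mean, SD or correlation. Assumed: baseline mean 20 or 25, SD 10; 12-week SD 12; correlation 0.3 or 0.5; scores rounded and cut to 0–60; success is a gain above 20 points. There were 4,000 replicates per setting (Monte Carlo error about 0.8 points). LR is the logistic likelihood-ratio test.

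| 70% vs 85% | Fisher | LR, unadjusted | LR, adjusted |
|---|---|---|---|
| mean 20, corr. 0.3 | 36.5% | 45.0% | 53.2% |
| mean 20, corr. 0.5 | 35.7% | 44.7% | 50.2% |
| mean 25, corr. 0.3 | 33.8% | 42.2% | 55.6% |
| mean 25, corr. 0.5 | 34.7% | 43.4% | 53.9% |

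A run of 2,000 replicates per setting gave 48.6–57.4% adjusted, so about 50–57% is a fair summary. For 40% vs 70% the figures are Fisher 83%, unadjusted 87–88%, adjusted 90–93%. At a common rate of 70% the adjusted test's simulated size was 5.2–5.5%. With a baseline mean of 30, success cannot exceed about 83%, so the 85% assumption is then unattainable.

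**6. Family-wise error of three pairwise tests at n = 50** (common rate 35–85%): Fisher at 0.05 gives 6.1–8.9%; Boschloo gives 9.0–12.0%.

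**The case against.** Much can be said for the plan as written.

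- Fisher's test controls its error rate, and the continuity-corrected sample sizes already allow for its conservatism. This stands. A reader might infer that the primary analysis is invalid or that the trial is too small for its two main comparisons; the exact powers above show neither.
- The loss is not material on every pair. Combination versus C-E drugs at the assumed rates loses almost nothing. This stands.
- Section 5.1 already concedes that combination versus rESWT lacks 80% power and treats it as pilot data. This stands too: no scenario tried brings that pair to 80%, so adjustment cannot be presented as a rescue.
- Much of the modelled gain comes from replacing a 3% test with a 5% test. For 70% vs 85% that step alone is worth 8–9 points in the table above; the covariate adds a further 5–13.
- Saying that baseline PSEQ is ignored would go too far, since success is a change from baseline. Section 5 also calls the five factors potential confounders only, and gives nothing on their prognostic strength.
- The size of about 3% presumes pairwise testing. A single 3×2 Fisher test would run at about 4.6%.

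What survives is narrower. A change score cut at a threshold does not adjust for baseline, least of all near a ceiling, and the plan has no other step that does.

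**Conclusion.** The point holds as a matter of efficiency and of protection from chance baseline imbalance, not of validity. The pairwise size of 2.4–3.5% and the Fisher-to-Boschloo gains (about 0, 0.9, 2.6 and 5.2 points for the four rows in step 3) are exact at 50 per arm and the plan's own rates. They rest only on pairwise testing and complete data.

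The 50–57% for combination versus rESWT rests on assumed PSEQ parameters, on the more-than-20-points definition and on a likelihood-ratio test. The power of the re-randomisation version proposed below was not computed. If baseline had no prognostic value, only the gain from replacing Fisher's test would remain. The change is worth making because the data are already planned, but the trial's two main comparisons do not depend on it.

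**What to change.** 1. Reconcile the success definition first (more than 20 points in Sections 4.11.1 and 5.1, more than 20 percent in Section 5), because the role of baseline differs between them.
2. For each pair, pre-specify logistic regression of success on arm and baseline PSEQ as the single covariate, or with very few covariates fixed in advance. At 70% vs 85% a pair has only about 50 × 0.30 + 50 × 0.15 = 22.5 failures, and with six covariates simulated type I error was 5.4–7.0%. Adding all five named factors is therefore unwise.
3. Report a standardised risk difference with 95% CI, and take the p-value by re-randomisation that respects the blocks of Section 4.9.
4. State that the success comparisons are pairwise and attach a multiplicity rule, for example Holm or a fixed sequence. Otherwise part of the recovered power is error rate that the family does not have.
5. Describe baseline characteristics, but do not rely on significance tests of them to handle imbalance.
6. If an unadjusted exact check is kept, use Boschloo's test under the same multiplicity rule.

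The cost is longer SAP wording, software other than the package named in Section 5, and some power returned to the multiplicity rule. No new data are needed.

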4.11.2. Secondary clinical outcomes

Secondary clinical outcomes will be:

[figure not shown]
- Numerical Rating Scale (NRS) score - The NRS will ask patients to rate their pain intensity on an 11-point scale where 0 indicates no pain and 10 indicates worst imaginable pain. The NRS score will be collected at baseline and at all follow-up examinations, i.e., two weeks, four weeks, 12 weeks and 24 weeks after baseline. A point score change of 4 points for the NRS score corresponds to the MCID (Maughan and Lewis, 2010). Note that according to

Maughan and Lewis (2010) the NRS score is least responsive in measuring clinically meaningful change in a chronic non-specific low back pain population.

- Oswestry Low Back Pain Disability Questionnaire (OLDPDQ) score (Fairbank and Pynsent, 2000; Davidson and Keating, 2001) – The OLDPDQ score is considered the ‘gold standard’ of low back functional outcome tools. The questionnaire is composed of ten sections (addressing pain intensity, personal care, lifting, walking, sitting, standing, sleeping, sex life, social life and travelling); for each section the possible score is 5 and, thus, the total possible score is 50. The final score is calculated as $[(\text{sum of individual scores}) / 50] * 100$ (%), and is interpreted as *minimal disability* (0% to 20%), *moderate disability* (21% to 40%), *severe disability* (41% to 60%), *crippled* (61% to 80%) or *patients are either bed-bound or exaggerating their symptoms* (81% to 100%). The OLDPDQ score will be collected at baseline and at all follow-up examinations, i.e., two weeks, four weeks, 12 weeks and 24 weeks after baseline. A point score change of 8 points for the OLDPDQ score corresponds to the MCID (Maughan and Lewis, 2010).

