- Patient Health Questionnaire 9 (PHQ-9) score (Kroenke et al., 2001) – The PHQ-9 will be used to assess depression. Patients will be asked how often, over the last two weeks, they had been bothered by the following problems: (i) little interest or pleasure in doing things; (ii) feeling down, depressed or hopeless; (iii) trouble falling or staying asleep, or sleeping too much; (iv) feeling tired or having little energy; (v) poor appetite or overeating; (vi) feeling bad about themselves, or that they are a failure or have let themselves or their family down; (vii) trouble concentrating on things, such as reading the newspaper or watching television; (viii) moving or speaking so slowly that other people could have noticed? Or the opposite – being so fidgety or restless that they have been moving around a lot more than usual; and (ix) thoughts that they would be better off dead or of hurting themselves in some way. For each potential problem the PHQ-9 score uses a 4-point scale where 0 = not at all, 1 = several days, 2 = more than half the days and 3 = nearly every day. The PHQ-9 score will be collected at baseline and at 12 weeks and 24 weeks after baseline.
- Lumbar curvature measurements performed on lateral lumbosacral spine radiographs – Chun et al. (2017) found a strong relationship between non-specific low back pain and decreased lumbar lordotic curvature in a recent meta-analysis based on 13 studies consisting of 796 patients suffering from non-specific low back pain and 927 healthy controls. Lateral X-rays of the lumbar spine will be taken in the standing position according to standard protocols in the literature (e.g., Chernukha et al., 1976; Marks et al., 2009; Been and Kalichman, 2014) and analyzed using Cobb’s angle, vertebral body and intervertebral

disc wedging, and facet joint angle (Fig. 3) (e.g., Been and Kalichman, 2014). Lumbar curvature measurements will be performed at baseline and at 12 weeks after baseline.

Fig. 3 (taken from Been and Kalichman, 2014). Measurements of lumbar lordosis Cobb's angle (LA), vertebral body (B) and intervertebral disc (D) wedging, and facet joint angle (F).

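### Secondary outcomes: the planned between-group tests name no use of the baseline value collected for each outcome, so they are valid but give up precision

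*Combined protocol and SAP*

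**What the plan says.** Section 5 describes the data for each secondary outcome in one sentence: "Each secondary clinical outcome will return a single data point at each time of follow-up examination". It then fixes a rank analysis for NRS, OLDPDQ and PHQ-9: "Comparison between groups will be performed using the nonparametric Kruskal-Wallis test followed by Dunns tests for pairwise comparisons". These scores are to be summarised by inter-quartile ranges.

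For Cobb's angle, vertebral body and disc wedging, and facet joint angles, a D'Agostino-Pearson test decides the analysis: "Comparison between groups will be performed with ANOVA followed by Bonferroni post tests for pairwise comparisons in case of passing the normality test", and otherwise Kruskal-Wallis with Dunn's tests, "in case of not passing the initial normality test".

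Section 4.11.2 shows that a baseline measurement exists for each outcome:

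- NRS: "The NRS score will be collected at baseline and at all follow-up examinations".
- OLDPDQ: "The OLDPDQ score will be collected at baseline and at all follow-up examinations".
- PHQ-9: "The PHQ-9 score will be collected at baseline and at 12 weeks and 24 weeks after baseline".
- Radiographic measures: "Lumbar curvature measurements will be performed at baseline and at 12 weeks after baseline".

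Section 5 names no baseline covariate, change score or adjusted model for any of them. It lists age, gender, body mass index, occupation and pain duration as potential confounders, but only compares these between groups. Baseline outcome scores are not on that list.

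**The concern.** A patient's baseline score usually predicts the later score to some degree. If the comparison ignores it, that predictable part of the spread between patients stays in the error term. The trial then pays for information it already holds and does not use.

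This matters most where the trial is thin. Section 5.1 accepts that combination therapy versus rESWT alone is underpowered on the primary responder endpoint (Table 8: 43.4% at 85% versus 70%) and offers that comparison as pilot data for a later study. Pilot data are most useful as effect estimates with intervals, and for the secondary outcomes Section 5 plans neither.

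For the radiographic measures there is a further, smaller matter: the analysis is not fixed, because a preliminary test on the trial's own data selects it.

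**Working it through.** **The plan's own figure.** The documents give no sample size or power for any secondary outcome. The figure they do give, 49 per group (Section 5.1, Table 9), is for the primary responder comparison at 70% versus 40%, two-sided 5%, power 0.8. It reproduces:

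- n = (1.960·√(2·0.55·0.45) + 0.842·√(0.21 + 0.24))² / 0.30² = 41.97, so 42 (Fleiss).
- With continuity correction: (41.97/4)·(1 + √(1 + 4/(41.97·0.30)))² = 48.4, so 49.

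The present point does not change it.

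**Inputs.**

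- 50 patients per arm (Section 4.9); two-sided 5% (Section 5.1).
- r, the baseline/follow-up correlation: not in the documents. Assumed 0.3, 0.5 and 0.7.
- Outcome SD: set to 1, so results are in SD units. The only pain-score spreads quoted (Table 3) carry the protocol's own query whether they are SD or SEM.
- Baseline values: taken as available from Section 4.11.2. Tables 5 and 6 do not tick the efficacy assessment at visit 1, but that column is headed as including the baseline assessment.

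**Precision under a linear model.** Residual variance with baseline as covariate is 1 − r². The equivalent increase in patients is 1/(1 − r²). The unadjusted standard error of a pairwise difference is √(2/50) = 0.20 SD. Power for a 0.5 SD difference (an illustrative size) is Φ(0.5/(0.20·√(1 − r²)) − 1.96).

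| r | 1 − r² | 1/(1 − r²) | 50 per arm is worth | power, 0.5 SD |
|---|---|---|---|---|
| 0 | 1.00 | 1.00 | 50 | 70.5% |
| 0.3 | 0.91 | 1.10 | 55 | 74.6% |
| 0.5 | 0.75 | 1.33 | 67 | 82.3% |
| 0.7 | 0.51 | 1.96 | 98 | 93.8% |

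**Same question on ranks.** The table compares linear analyses, so it does not itself measure Kruskal-Wallis against an adjusted analysis. A simulation does: three arms of 50, whole-number scores from 0 to 10, shifts of 0, 0.25 and 0.5 SD, 4,000 runs per setting.

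- Kruskal-Wallis on follow-up values: power 55% to 56% at every r.
- Rank-based ANCOVA on baseline: about 55%, 59%, 68% and 80% at r = 0, 0.3, 0.5 and 0.7.
- With no true difference, Kruskal-Wallis rejected in 4.3% to 5.3% of runs.

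**Chance imbalance.** With 50 per arm, a baseline difference between two arms also has standard error 0.20 SD. Only r times that difference passes into the follow-up comparison. A one-standard-error imbalance therefore shifts it by 0.06, 0.10 or 0.14 SD at r = 0.3, 0.5 or 0.7. An imbalance above 0.4 SD arises in 4.6% of trials for a given pair and outcome. At exactly 0.4 SD the shift is 0.12, 0.20 or 0.28 SD.

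**The case against.** **Follow-up values are inferred.** The plan does not say that unadjusted follow-up values are compared. A single data point per visit could be a change from baseline, and Section 4.11.1 defines treatment success as an improvement. This stands as a limit: comparing follow-up values is the natural reading of Section 5, not its wording. It does not remove the point. If change scores were meant, the section should say so. With equal variances at both times, their variance is 2(1 − r) = 1.4, 1.0 and 0.6 at r = 0.3, 0.5 and 0.7, against 0.91, 0.75 and 0.51 with baseline as covariate.

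**The rank test itself is defensible.** A reader might fault the plan for declaring the scores non-normal in advance. Fixing a rank test beforehand for bounded, discrete scores is prespecification. The pre-test criticism applies only to the radiographic measures.

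**The MCIDs are not a direct yardstick.** A reader might infer that results must be set against the 4 points (NRS) and 8 points (OLDPDQ) in Section 4.11.2. Both are stated as point score changes, and a difference between arms is another quantity. Section 4.1 also says the design considers the quality-scale items, which include point estimates and measures of variability. So effect reporting is not wholly neglected, although Section 5 names no between-group difference or interval for these outcomes.

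**A linear mixed model is not the only remedy.** Rank-based ANCOVA uses baseline and keeps the nonparametric approach. PHQ-9 may also be skewed towards low values, since Section 4.5 excludes psychiatric disorders. The choice between these models is partly preference.

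**Conclusion.** The point holds as one of efficiency. The planned comparisons name no use of baseline, and they give up the share r² of outcome variance that baseline could explain: 9%, 25% or 49% for r = 0.3, 0.5 or 0.7. The size rests wholly on r, which is assumed. At r = 0.3 the gain is modest, and at r = 0 there is none.

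A reader might infer that the plan is biased or that its false-positive rate is inflated. The documents do not support that. Randomisation makes the unadjusted tests valid, with overall type I error near 5%. In a trial that happens to have a 0.4 SD imbalance, the conditional error would be 8.1%, 13.4% or 21.7% at the three values of r. Trials with small imbalance offset this: at 0.2 SD it is 5.0%, 4.8% or 3.9%. Nor is chance imbalance a second harm to add to the lost precision; both are the same r² share of variance.

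Only secondary outcomes are affected, and every power statement in Section 5.1 concerns the responder endpoint and is untouched. The change is worth making because it needs no new data.

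**What to change.** Amend Section 5 before any comparison of the arms:

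- State for every secondary outcome that its baseline value enters the analysis as a covariate.
- Radiographic measures: ANCOVA at week 12 with treatment and baseline, without the normality pre-test.
- NRS, OLDPDQ and PHQ-9: name one method in advance. This can be a baseline-adjusted repeated-measures model with visit and visit-by-treatment terms, or a rank-based ANCOVA at each visit.
- Report pairwise between-group differences with 95% confidence intervals. A rank test does not supply these by itself, so if that route is taken, name the estimate to be reported beside it.
- Keep the unadjusted Kruskal-Wallis test as a sensitivity analysis.

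The cost is SAP wording, slightly more analysis work, and possibly naming software other than the GraphPad Prism 5 given in Section 5. No extra patients, visits or measurements are needed.
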